7.1.3.2 Per-Protocol Analysis Dataset

Per-protocol analysis dataset is the subset of the primary analysis dataset. Per-protocol analysis will be performed for the subjects who received the treatment of the PRESTIGE LP™ investigational devices at two contiguous levels but had no major protocol deviations, such as violation of inclusion and exclusion criteria or receiving different treatments other than intended treatment. Per-protocol analysis will only be carried out for overall success status.

7.2 General Methodology

7.2.1 Laboratory Data and Analysis

Data of the metal concentrations in serum generated by the labs will be documented and provided to Medtronic, and the summary statistics (n, mean, median, standard deviation, minimum and maximum) at each time point will be presented. The changes in metal concentrations from preoperative at each post-operative visit will be analyzed using paired t-test for normally distributed data or Wilcoxon signed rank test for not normally distributed data. Further analysis on simple correlation of the metal concentration with continuous clinical outcome scores (NDI, neck pain, arm pain, and SF-36 PCS) and subgroup analysis on the metal concentrations by binary outcomes (neurological success, NDI success and overall success) will be carried out.

7.2.2 Clinical Data and Analysis

For continuous clinical outcome scores such as NDI, neck pain, arm pain, SF-36 PCS, and surgery data, the summary statistics (n, mean, median, standard deviation, minimum and maximum) at each time point will be presented. The changes from preoperative at each postoperative visit will be analyzed using paired t-test for normally distributed data or Wilcoxon signed-rank test for not normally distributed data.

For categorical clinical outcomes such as overall success, neurological status, NDI success, and pain medication use, frequency and percentage of subjects will be summarized at each time point.

For secondary surgery and adverse events, the rates will be summarized using the life-table method of time-to-event analysis. The Kaplan-Meier analysis will be applied to return-to-work summary.

7.3 Center Pooling

Data collected from different investigational sites will be pooled.

7.4 Handling of Missing Data and Dropouts

Missing data due to missed follow-ups, lost to follow-ups (dropouts), or failure to answer CRF questions during office visits will not be imputed for analyses. Therefore, only observed data are analyzed.

7.5 Adjustments for Multiple Comparisons

No adjustments for multiple comparisons will be made.

7.6 Demographic and Other Baseline Characteristics

Demographic and other baseline variables will be summarized with descriptive statistics. For continuous variables such as age, height and weight, the summary statistics including n, mean, standard deviation, median, and minimum and maximum, will be presented. For categorical variables such as race and gender, frequency and percentage of the subjects in each category, will be summarized.

7.7 Interim Analyses

No interim analysis will be conducted for this study.

7.8 Evaluation of Objectives

7.8.1 Primary Objective and Primary Measurement Analyses

The primary objective of this study is to assess the concentrations of Titanium (Ti), Vanadium (V), and Aluminum (Al) in the blood serum of patients implanted with the PRESTIGE LP™ Cervical Disc at two contiguous cervical levels. The primary measurement analyses associated with the primary objective include:

- The metal concentrations of Titanium (Ti), Vanadium (V), and Aluminum (Al) at preoperative, 6 weeks, and 12 months after index surgery. The summary statistics including n, mean, median, standard deviation, minimum and maximum will be summarized.
- The summary statistics for the changes in the metal concentrations from preoperative will be presented, and the two-sided paired t-test for normally distributed data or Wilcoxon signed-rank test for not normally distributed data will be performed.
- The summary for titanium concentrations from this study will be presented side by side with the one from the Prestige LP™ one-level metal study.
- Pearson correlation analysis will be carried out between the metal concentrations and continuous clinical outcome variables including NDI, arm pain, neck pain, and SF-36 PCS scores at postoperative time points.
- Subgroup analysis of the metal concentrations by binary outcomes including overall success, NDI success and neurological success will be carried out. No statistical inference will be made.

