#### **Medtronic Controlled Information**

- Collect information on permanent metal implants, exposure to metal ions in working environment and injections, supplements and/or vitamins containing titanium, aluminum and vanadium.

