### 6.1 Treatment Groups

All subjects enrolled in this study will receive the same treatment with the Prestige LP™ Cervical Disc at two contiguous levels. Data will be collected from subjects with conditions, medical history or environments that would contribute to additional metal ion exposure. This includes subjects working in a profession where exposure to metal ions may be increased, subjects taking injections or supplements containing metal ions or subjects who have permanent metal implants. No subjects will be randomized for this study.

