## **13 Statistical Design and Methods**

Since there is not statistical hypothesis, the analyses will be descriptive in nature. In general, the categorial variables will be summarized using frequency tables and continuous variables will be summarized using mean, standard deviation, median, minimum, and maximum.

All data analyses will be based on observed data; missing data will not be imputed.

Changes in metal concentration and other scores from preoperative will be assessed by using paired t-test for normally distributed data or Wilcoxon signed rank test for not normally distributed data.

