#### **13.1.2 Secondary Measurement Analysis**

For secondary measurement, including overall success, NDI success and neurological success, success rate will be summarized in frequency tables. The success rate at other visits will also be summarized. In addition, change of NDI score, neck pain score and SF-36 PCS score at post-op visits from baseline will be summarized using mean, standard deviation, median, minimum and maximum. Paired t-test or Wilcoxon signed rank test will be carried out to test whether the change from the baseline is significant.

The relationship between the metal concentration and clinical variables will be assessed at the end of the study. Simple correlation analysis will be performed for the relationship between metal concentrations and continuous outcome scores, including NDI, neck pain, arm pain and SF-36 PCS scores by evaluation time point. The relationship between metal concentrations and binary outcomes, including overall success and neurological success will be assessed by comparing metal concentrations in the success and failure groups of subjects' statuses by evaluation time point.

The cumulative rate of AEs and secondary surgeries will be derived using survival analysis.

---

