## Established Performance Goals

The Allowable Total Error for this method is set at 20%. Performance goals for both accuracy and precision are set at 10%. Method validation studies were performed to determine the following performance parameters of this method, and are detailed in section 9 of this document.

- Limit of Quantitation

The limit of quantitation was determined following CLSI guideline EP17-A2 and is set at 0.3 ng/mL for Ti.

- Accuracy

Recovery - As determined by a recovery study in serum matrix, the systematic error for titanium is -2.49% and for vanadium is -1.78%, within an allowable systematic error of 10%.

- Inter-lab Corroboration – Accuracy

The TMAL performed an inter-lab comparison of values with Mayo Medical Laboratories (MML), Rochester, MN in 2013. Serum samples from 15 subjects were tested by both the laboratories. The samples were collected from 2011 through 2013; the integrity of the samples was maintained by following the TMAL collection and storage protocol. Analyte concentrations of the samples ranged from 1 to 40 ng/mL for Ti and from 0.01 to 17 ng/ml for V.

MML provided results following their standard protocol using DRC-ICP-MS for Titanium, as well as ICP-OES for Titanium.

The TMAL tested the samples across 11 different runs from 2011 through 2013 using method of additions. The calibrators were made from inorganic titanium and vanadium standard of purchased from High Purity Standards.

Comparing TMAL and MML's resulted in the following linearity. For Titanium using DRC-ICP-MS,  $r^2=0.9976$ , slope=1.0455, and using ICP-OES,  $r^2=0.994$ , slope=0.980. For Vanadium using DRC-ICP-MS,  $r^2=1$ , slope = 0.9559.

- Reference Material Accuracy

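### SAP 7.8.1 plans only Pearson correlation between serum metals and clinical scores; adding Spearman and marked scatter plots would show when one subject drives the coefficient

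*SAP*

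**What the plan says.** SAP 7.8.1 lists, among the primary measurement analyses, "Pearson correlation analysis will be carried out between the metal concentrations and continuous clinical outcome variables". The scores are NDI, arm pain, neck pain and SF-36 PCS, at postoperative time points. No transformation, rank method, plot or check for influential values is named. Use of untransformed concentrations is therefore the natural reading, not a stated one.

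The other two places leave the type of correlation open. SAP 7.2.1 asks for "simple correlation of the metal concentration with continuous clinical outcome scores". Protocol 13.1.2 says: "Simple correlation analysis will be performed for the relationship between metal concentrations and continuous outcome scores".

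For changes in concentration from baseline, SAP 7.8.1 does provide for non-normal data: "two-sided paired t-test for normally distributed data or Wilcoxon signed-rank test for not normally distributed data will be performed".

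Protocol 6.1 expects some subjects to carry metal from other sources. It names occupational exposure and "subjects taking injections or supplements containing metal ions or subjects who have permanent metal implants". None of exclusion criteria E.1 to E.19 removes them. Protocol 5.2.3 adds the data item: "Collect information on permanent metal implants, exposure to metal ions in working environment and injections, supplements and/or vitamins containing titanium, aluminum and vanadium". Neither Protocol 13.1.3 nor SAP 7.8 names an analysis that uses it.

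Protocol 13 sets the status of all this: "Since there is not statistical hypothesis, the analyses will be descriptive in nature".

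**The concern.** Pearson weights each subject by distance from the mean concentration. If one subject's serum metal comes largely from another source, that subject can supply most of the variation in metal, and the coefficient then mostly describes that subject. A real association across the others would be reported as weak. The plan foresees both non-normal metal data and exposed subjects, but the correlation has no companion that would reveal the problem.

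The stake is modest. No decision rule hangs on these coefficients. They do bear on how the metal data are read for safety, and Protocol 10.2 gives the assessment of potential safety concerns from metal in the blood as the benefit of the study.

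**Working it through.** **The plan's own figure.** There is none to reproduce. SAP 6 gives 30 subjects without an effect size, SD, alpha or power. Protocol 8.5 does not replace withdrawals, so each correlation has at most 30 pairs.

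**Number of correlations.** 3 metals × 4 scores × 2 postoperative blood draws (6 weeks, 12 months) = 24.

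**Model.** The following are assumptions, because the documents give no serum distribution for this population:
- metal = exp(ln(GSD)·z), with geometric SD (GSD) 1.5, 2 or 3
- score = ρz + √(1−ρ²)·e, with z and e standard normal and ρ = 0.5, so the score is linear in log metal
- one subject's metal is multiplied by 5 or 10 and that subject's score is unchanged, so the extra metal has no bearing on outcome
- n = 30, 20,000 runs per setting

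Pearson is computed on the concentrations. Spearman is the same formula on ranks. Detection means two-sided p < 0.05 and serves only as a yardstick.

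**Result under this model.** Detection in per cent, Pearson v Spearman:

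| One subject's metal | GSD 1.5 | GSD 2 | GSD 3 |
|---|---|---|---|
| unchanged | 80 v 78 | 75 v 77 | 66 v 77 |
| ×5 | 30 v 70 | 51 v 72 | 56 v 75 |
| ×10 | 9 v 71 | 27 v 71 | 42 v 73 |

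Median coefficients at GSD 2 (unchanged, ×5, ×10) are 0.47, 0.37 and about 0.25 for Pearson, and 0.48, 0.46 and 0.45 for Spearman. At ×10 and GSD 2, leaving that subject out moves Pearson by a median of 0.20 and Spearman by 0.04.

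**Why.** The subject's share of the metal sum of squares is (x₁−x̄)²/Σ(xᵢ−x̄)². Its median at GSD 1.5 / 2 / 3 is 70 / 36 / 7% for ×5 and 90 / 74 / 33% for ×10. On ranks the most that one of 30 subjects can carry is 14.5² / [(30³−30)/12] = 210.25 / 2247.5 = 9%.

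**Result when the model is changed.** The ranking of the two methods is not stable (detection in per cent, Pearson v Spearman):
- Score linear in raw metal, no exposed subject: 80 v 70, 75 v 59 and 61 v 36 at GSD 1.5, 2 and 3. Spearman loses 10, 16 and 25 points.
- Score follows total serum metal, one subject ×10: log-linear 95 v 87 (GSD 1.5) and 80 v 85 (GSD 2); raw-linear 96 v 72 (GSD 2). The exposed subject does not mask the link.

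**No true link.** With one subject at 10 times the median and an independent score, both methods reach p < 0.05 in about 5% of runs. If that subject's score also happens to lie 2 SD high, the median coefficient at GSD 2 is 0.31 for Pearson and 0.09 for Spearman.

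**What the documents offer on spread.** In Protocol Appendix I (inter-laboratory comparison, 15 subjects): "Analyte concentrations of the samples ranged from 1 to 40 ng/mL for Ti and from 0.01 to 17 ng/ml for V". If titanium were lognormal, a 40-fold range in 15 values implies ln(40)/3.472 = 3.689/3.472 = 1.06, so GSD = exp(1.06) ≈ 2.9. Here 3.472 is the expected range of 15 normal values in SD units. The population and the selection of those samples are not stated, and they may have been chosen to span a range. This is at best an upper guide.

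**The case against.** The strongest case against is that the large gaps depend on two modelling choices. The score is made linear in log metal, which favors ranks, and the exposed subject's extra metal is made irrelevant to outcome, which builds masking in. The planned analysis relates total serum concentration to the scores, and no passage says on which scale the two are linked or whether the source of the metal matters. This stands. A reader might infer that Pearson is the wrong method and that Spearman should replace it at almost no cost. The documents do not support that, because under a raw-linear relation Spearman loses 10 to 25 points of detection and could itself hide a link.

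Next, the only spread in the documents points to a GSD near 3. There a ×5 subject carries a median of 7% of the metal sum of squares, and Pearson detection falls only from 66 to 56%. This also stands. The documents do not show that one subject would dominate, and they support neither the ×5 nor the ×10 multiplier.

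Finally, the analysis is descriptive, Pearson is a permissible form of simple correlation, and the planned minimum and maximum would expose an extreme value. The subgroup summaries by success status give a second view of association. All true, but none of these shows whether the extreme value belongs to an exposed subject or how far it moves the coefficient. That narrower gap remains.

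**Conclusion.** The point holds as a minor, cheap improvement. A lone Pearson coefficient on about 30 subjects cannot tell the reader whether it describes the cohort or one subject, and the protocol itself makes such a subject foreseeable. The illustrative size is a median of about 0.25 for Pearson against 0.45 for Spearman. It rests on lognormal metal with GSD 2, a true log-scale correlation of 0.5, and one subject raised tenfold by metal unrelated to the score. With a different spread, multiplier or link the gap shrinks or reverses.

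Two further inferences are not supported. SAP 7.8.1 does not conflict with the protocol, since it only makes a general term specific. Nor does an exposed subject raise the false-positive rate in general: it stays near 5% for both methods unless that subject's score also happens to be extreme.

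**What to change.** In SAP 7.8.1, and for consistency in 7.2.1:
- keep Pearson and report Spearman beside it for each metal, score and postoperative blood draw
- show a scatter plot for each pair and visit, marking subjects whose other metal exposure is recorded under Protocol 5.2.3
- state in advance that a marked disagreement between the two coefficients will be read as a sign that one or a few subjects, or a non-linear relation, drive the result, with the plot used to tell which

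The cost is 24 more descriptive coefficients (24 + 24 = 48 in all), the plots and a few lines of code. No new subjects, samples or visits are needed, and Protocol 13.1.2 can stand as written. Fixing this before the data are seen also avoids a later choice between coefficients.

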7.8.2 Secondary Objectives and Secondary Measurement Analyses

The secondary objectives of this study are to evaluate overall success, NDI score and success, neurological success, neck pain score and success, arm pain score and success, SF-36 PCS scores and success, secondary surgery, and adverse events.

7.8.2.1 Overall Success

Overall success is claimed when the following four conditions are met:

- Postoperative NDI score improvement of at least 15 points from preoperative;
- Maintenance or improvement in neurological status;
- No serious, implant or implant/surgical procedure associated adverse event; and
- No secondary surgical procedure classified as “failure”.

Frequency and percentage of overall success at postoperative time points will be summarized, and no statistical conclusion will be drawn.

7.8.2.2 NDI Score and Success

The summary statistics including n, mean, median, standard deviation, minimum and maximum for NDI score and change from preoperative will be summarized. The paired t-test for normally distributed NDI score or Wilcoxon signed-rank test for not normally distributed NDI score will be carried out to test whether the change from preoperative is significant.

NDI success is defined as follows:

Preoperative score – Postoperative score ≥ 15 .

The frequency and percentage of NDI success status will be summarized, and no statistical inference will be made.

7.8.2.3 Neck Pain

Neck pain is composed of pain intensity and duration, and its score is the sum of the numerical ratings of both. The summary statistics including n, mean, median, standard deviation, minimum and maximum for neck pain score at all visits and change at postoperative visits from preoperative will be summarized. The paired t-test for normally distributed pain score or Wilcoxon signed-rank test for not normally distributed pain score will be performed to test whether the change from preoperative is significant.

Neck pain success is defined as follows:

Preoperative score – Postoperative score > 0 .

The frequency and percentage of neck pain success status will be summarized, and no statistical inference will be made.

7.8.2.4 Arm Pain

Arm pain consists of pain intensity and duration, and its score is derived by adding the numerical ratings of both. The summary statistics including n, mean, median, standard deviation, minimum and maximum for arm pain score at all visits and change at postoperative visits from preoperative will be summarized. The paired t-test for normally distributed pain score or Wilcoxon signed-rank test for not normally distributed pain score will be performed to test whether the change from preoperative is significant.

Arm pain success is defined as follows:

Preoperative score – Postoperative score > 0.

The frequency and percentage of arm pain success status will be summarized, and no statistical inference will be made.

7.8.2.5 SF-36 PCS

The component of SF-36, PCS, is derived from the self-evaluated questionnaires based on the algorithm formulated by the Medical Outcomes Trust, the developer of the SF-36 survey form. The summary statistics including n, mean, median, standard deviation, minimum and maximum for PCS score at all visits and change at postoperative visits from preoperative will be summarized. The paired t-test for normally distributed PCS score or Wilcoxon signed-rank test for not normally distributed PCS score will be performed to test whether the change from preoperative is significant.

PCS success is defined as follows:

Postoperative score - Preoperative score ≥ 0 .

The frequency and percentage of PCS success status will be summarized, and no statistical inference will be made.

7.8.2.6 Neurological Success

Success of each element is defined as maintenance or improvement from preoperative. Failure of each element is defined as deterioration from preoperative. Success of each neurological component (Motor function, Sensory function, or Reflexes) is defined as success of all elements, and failure of each component is defined as failure of at least one element. Success of overall neurological status is defined as success of all three components, and failure as failure of at least one component. Frequency and

percentage of each component as well as overall neurological success status will be summarized, and no statistical comparisons will be carried out.

7.8.2.7 Secondary Surgical Interventions

A time-to-event analysis (life-table method) will be carried out to summarize the secondary surgeries including revision, removal, supplemental fixation, reoperation, and other categories.

7.8.2.8 Adverse Events

Causality of AEs is categorized as implant associated, surgical procedure associated, implant/surgical procedure associated, undetermined, or not related. AE severity is characterized into four categories: mild (Grade 1), moderate (Grade 2), severe (Grade 3), and life-threatening (Grade 4). For a conservative consideration, implant or implant/surgical procedure associated AEs are considered to be implant associated. Analysis using life-table method will be carried out for all adverse events, implant or implant/surgical procedure associated AEs, Grade 3 or Grade 4 AEs, and Grade 3 or Grade 4 AEs that are implant or implant/surgical procedure associated. In addition, serious adverse device effect (SADE) will be summarized if available.

7.8.3 Other Measurement Analyses

7.8.3.1 Work Status

Work status is classified as currently working and not working. Frequency and percentage of subjects at each time point will be summarized, and no statistical inference will be made.

7.8.3.2 Pain Medication Use

Pain medications are categorized as Non-Narcotic Medications, Weak Narcotic Medications, Strong Narcotic Medications, and Muscle Relaxant Medications. There are five values listed for frequency of usage in each category of the medication use. Frequency and percentage of subjects in each value listed for frequency of usage of the medication use will be summarized, and no statistical inference will be made.

7.8.3.3 Surgery Data

Estimated blood loss, length of surgery, and length of hospital stay (calculated from date of surgery until date of discharge) will be summarized, and the summary statistics including n, mean, median, standard deviation, minimum and maximum will be presented.

7.8.3.4 Return to Work

Return to work based on the first date on which a subject returned to his/her job duty after surgery will be analyzed using Kaplan-Meier method. The median return to work time (in days) will be calculated.

